 - ii. Cases in which the subject has a solitary or horseshoe kidney
 - iii. Cases in which the subject has more than two masses in the applicable kidney
 - iv. Cases involving a bilateral operation

III. **STUDY ENDPOINTS.** The Primary and Secondary Endpoints are described on **Exhibit A**. For both the Control Cases and the Intervention Cases (as such terms are defined in Section IV below):

- a. All Primary Endpoints (except Total Operative Time) will be measured by review of the video case recording; and
- b. All Secondary Endpoints and Total Operative Time will be measured using data derived from the EHR.

IV. STUDY DURATION, CASES AND STATISTICAL MODEL

a. Study Duration

This study will commence as soon as practicable following IRB approval, and will end on the earlier of (i) the date on which all Intervention Cases have been performed, as more fully detailed below, and the researchers have completed all associated statistical analysis or (ii) March 31, 2019.

b. Intervention Cases

The set of intervention cases ("*Intervention Cases*") will be all operations:

- That meet the criteria set forth in Section II above;
- Are performed by the surgeons participating in the study;

- Which occur after commencement of the study, until such time as the calculated number of Intervention Cases (as discussed more fully below) have been completed; and
- Which are identified Intervention Cases as discussed in subsection (d) below.

The calculated number of Intervention Cases is set forth on **Exhibit A**. approach used to calculate such number is detailed in subsection (d) below (Randomization, Blinding and Sample Size Calculation)..

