Interims computations of sample size will be performed to ensure the study maintains 70% power to detect a 10% difference in the primary endpoint with use of the appropriate statistical test. An interim computation will occur when ½ of the cases have completed the protocol. The interim computations 1) will involve only interim estimates of standard deviations of interest along with their corresponding 95% confidence intervals, 2) will be blind to whether “Group 1” or “Group 2” was to the VR-aided method, and 3) will not reveal to the surgeons or patients any information about magnitudes of group differences. If power is deemed inadequate, the sample size will be adjusted in both the number of Control Cases and Intervention Cases accordingly. This will be accomplished by repeating the sample size calculation described in Section IVd with data from the ongoing study. Adjustments to sample size are anticipated to be relatively small in relation to the large overall sample size.

c. Control Cases

The set of control cases (“*Control Cases*”) will be all operations:

- That meet the criteria set forth in Section II above;
- Are performed by the surgeons participating in the study;
- Which occur after commencement of the study, until such time as the calculated number of Control Cases (as discussed more fully below) have been completed; and
- Which are identified as Control Cases as discussed in subsection (d) below.

Sample size for Intervention Cases has been calculated based on the methodology described above, and Control Case sample size shall be calculated using a 1:1 group ratio.

d. Randomization, blinding, and sample size calculation

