Eligible subjects identified from the medical record will be those who are 1) scheduled to undergo RALPN surgery, 2) willing to consent to the surgery being performed by one of the four surgeons participating in the study, and 3) willing to be assigned by randomization to a preparation method (VR-aided or control). Each case will be assigned to one of the two preparation methods by a randomization procedure that is stratified by surgeon (four separate surgeon-specific randomization schedules.) Each surgeon-specific randomization schedule will be prepared using permuted blocks of size 2; i.e., each 2-patient block will be some permutation of {VR-aided, Control}. Thus, each surgeon’s cases will be randomized in a 1:1 ratio. Use of permuted blocks thus avoids any confounding of preparation method with temporal trends (e.g., trend due to a learning curve.) Approximately 20 sequentially numbered opaque sealed envelopes (SNOSEs) will be prepared for each individual surgeon, each containing the treatment assignment for one case, and will provided to the Research Coordinator. The treatment code will remain concealed inside the envelope until

the moment the case is ready to be prepared. Patients, personnel gathering data from the video review, and statistician will be blinded. Control and intervention groups identifiers will be known only to the research personnel opening the sealed envelope for random group assignment and extracting patient data from the electronic medical record.

We calculated the sample size based on our pilot data of the total operative time, which shows an effect size of 0.44 regarding the difference of total operative time between VR-aided and control groups. We took the within-surgeon correlation to be 0.3. We use data from the most-of-interest variable (aka total operative time). To account for the within-cluster correlation, we adopted the sample size calculation method proposed in [1]. We took three values of within-cluster correction ($\rho = 0.3, 0.5, 0.7$) to consider low/moderate/high levels of within cluster correlation. In order to account for multiple endpoints and some other unpredictable factors, we propose to raise the sample size by 15%. We selected $\rho=0.3$ given the wide variation in case complexity seen in our pilot study, which drastically limited within-cluster clustering. Our target sample size using this method is 78 patients.

	$\rho = 0.3$	$\rho = 0.5$	$\rho = 0.7$
Before adjustment	34	39	47

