After 15% adjustment	39	45	54

[1] Diggle, P. J., Heagerty, P., Liang, K. Y., and Zeger, S. L. (2002). Analysis of Longitudinal Data. New York: Oxford University Press.

e. Statistical Model

Baseline values (means, standard deviations and proportions) will be tabulated together with corresponding confidence intervals (CIs) for each primary endpoint in both the Control Cases and Intervention Cases based on relevant historical data. For primary endpoints of various operative times, the nonparametric Wilcoxon signed rank test will be utilized to calculate the sample size needed to have 70% power to detect a 10% difference. False Discovery Rate (FDR) control will be enforced by using Benjamini-Hochberg procedure at the level of 5% in order to account for multiple testing issue.

Statistical analysis will include standard comparison of baseline endpoints between VR-aided and control groups with the appropriate statistical tests depending on the type of outcomes. For continuous outcomes (e.g. various operative times), the nonparametric Wilcoxon signed rank test will be used for comparison, which does not rely on the normality assumption. For binary outcomes (e.g. Mortality), Fisher's exact test will be used. P-values of all tests will be reported. The threshold of rejecting null hypothesis will be chosen at the conventional level of 0.05. Tests fail to be rejected will be reported as inconclusive. To study the adjusted difference between case/control group, we will also use generalized linear mixed model to regress the endpoint variables on Surgical and Clinical covariates listed in **Exhibit A**, where random effects will be imposed on surgeon clusters. Depending on the type of outcome, the linear mixed model (for continuous outcome) or the logistic mixed model (for binary outcome) will be used. To ensure normality, the continuous outcome will be Box-Cox transformed. In the regression analysis, we also use model diagnosis tools, such as QQ-plots to ensure various assumptions for the regression model are met. In

addition, to test the reliability of our model, we will also perform sensitivity analyses by splitting data into training and test set and perturb various assumptions (such as normality assumption and the Box-Cox transformation) in the regression model and inspect how well the results can be reproduced. The repeated measure ANCOVA will be used to test the adjusted difference between case/control groups.

V. SURGEON SURVEYS

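### Section IV.e names a paired test for continuous outcomes but no pair is defined, so the test cannot be run as written

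*Combined protocol and SAP*

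**What the plan says.** Section IV.e (Statistical Model) of the combined protocol and SAP names the signed rank test twice. For the analysis: "For continuous outcomes (e.g. various operative times), the nonparametric Wilcoxon signed rank test will be used for comparison". For sample size: "the nonparametric Wilcoxon signed rank test will be utilized to calculate the sample size needed to have 70% power to detect a 10% difference". The same analysis paragraph gives binary outcomes an independent-groups test: "For binary outcomes (e.g. Mortality), Fisher's exact test will be used".

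The interim computation in IV.b leaves the test open, asking for "70% power to detect a 10% difference in the primary endpoint with use of the appropriate statistical test".

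Section IV.d randomises each surgeon's cases on a separate schedule in which "each 2-patient block will be some permutation of {VR-aided, Control". The reason given concerns allocation, not analysis: "Use of permuted blocks thus avoids any confounding of preparation method with temporal trends (e.g., trend due to a learning curve".

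Section III adds: "All Primary Endpoints (except Total Operative Time) will be measured by review of the video case recording". In Exhibit A that makes four of the five primary times for this operation dependent on a usable recording. Total operative time comes from the health record.

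**The concern.** A signed rank test ranks the differences between two members of a pair. Here each patient contributes one value per endpoint to one arm, so an analyst must first decide which VR-aided case goes with which control case. The plan is silent on this, and its other statements point different ways. The blocks of 2 suggest block pairs. Fisher's exact test in the same paragraph suggests independent groups and hence possibly a rank-sum test.

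The choice has consequences. Some readings use the stratification by surgeon and some discard it, which changes power and the true error rate. Even the two sound readings will not always give the same verdict. A block in which one case has no usable value, or which is still open when a surgeon stops, also needs a rule before it can enter a paired test.

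**Working it through.** **Inputs.** From IV.d: 39 per arm (78 in total), four surgeons, blocks of 2, within-surgeon correlation ρ = 0.3, effect size d = 0.44. From IV.e: level 0.05. Assumed: two-sided testing, normal outcomes, and one endpoint before the Benjamini-Hochberg step. IV.d does not say which SD underlies 0.44. The total SD is used first, then the within-surgeon SD.

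**The plan's own figures.** 34 × 1.15 = 39.1, rounded to 39, and 2 × 39 = 78, so these steps reproduce. The 34 cannot be rebuilt from the stated inputs because no cluster size is given.

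**Does the sample-size table reveal a paired test?** For within-surgeon pairs at 70% power, the number of pairs is 2(z₀.₉₇₅ + z₀.₇₀)²(1 − ρ)/d², divided by 3/π = 0.955 for the signed rank test. With (1.960 + 0.524)² = 6.17:

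- ρ = 0.3: 2 × 6.17 × 0.7/0.1936 = 44.6; 44.6/0.955 = 46.7, so 47 pairs
- ρ = 0.5: 34 pairs
- ρ = 0.7: 21 pairs

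The paired requirement falls as ρ rises (47, 34, 21). The plan's unadjusted figures rise (34, 39, 47). The table therefore does not size a test on within-surgeon pairs and cannot be used to infer one.

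**Power by formula at 39 per arm, d on total SD.**

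- Block pairs: the difference has variance 2(1 − 0.3) = 1.4, so 0.44/√1.4 × √39 = 2.32. Multiplying by √0.955 gives 2.27. Power is about Φ(2.27 − 1.96) = 0.62, before small-sample loss.
- Pairs that ignore surgeon, or an unstratified rank-sum test: 0.44/√2 × √39 = 1.94. Multiplying by √0.955 gives 1.90. Power is about Φ(1.90 − 1.96) = 0.48.

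**Simulation** (surgeon variance 0.3, residual 0.7; 20/20/20/18 cases per surgeon; complete data; 15,000 to 40,000 trials per setting):

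| Reading of the test | Power, d = 0.44 on total SD | Rejection under the null |
|---|---|---|
| Signed rank, block pairs | 60% | about 5% |
| Surgeon-stratified rank-sum (van Elteren) | 59% | about 5% |
| Signed rank, pairs ignoring blocks | 48% | about 3% |
| Unstratified rank-sum | 49% | about 3% |

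Block pairs and van Elteren disagree on p < 0.05 in 9.9% of trials at d = 0.44. With d on the within-surgeon SD, power is 46% for block pairs, 45% for van Elteren and 35% for pairs ignoring blocks.

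**Incomplete blocks and trends.** The documents give no missing-data rate and no trend size, so these figures only illustrate the trade-off between the two sound tests. With 5% of values missing at random, block pairing discards about 78 × 0.95 × 0.05 = 3.7 observed patients, and power is 55% against 57% for van Elteren. With 10% missing it discards 78 × 0.9 × 0.1 = 7.0, and power is 50% against 54%. An assumed linear decline of 1 SD over each surgeon's series, with complete data, reverses the order: 60% for block pairs and 54% for van Elteren.

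**The case against.** The best defence is that the plan does name a test, and names it twice. Every completed block contains exactly one VR-aided and one control case of the same surgeon, so a signed rank test on block differences fits the randomisation. This stands. That reading holds its level and loses no power with complete data. The blocks can also be recovered. The envelopes are numbered, and the first REDCap form in VII.a holds surgeon number and operation date, although date is only a proxy for envelope order.

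What the defence does not supply is the link. IV.d gives protection against time trends as the purpose of the blocks, the binary outcomes get an unpaired test, and the sample-size table behaves unlike a paired calculation. The reader has to guess.

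A reader might go further and infer that the test can only be chosen after the data exist, or that false positives are inflated. The documents do not support either. Nothing prevents the definition from being added before data by group are seen. Inflation arises only if someone computes two tests and reports the smaller p-value, which no section proposes. Even then its size depends on the supposed alternative: about 6.4% with van Elteren and complete data, which the plan never mentions, and about 5.4 to 5.6% with a plain rank-sum test. A figure as high as 7.4% needs 10% missing values and an open block for all four surgeons as well. Blinding of the statistician ("Patients, personnel gathering data from the video review, and statistician will be blinded") would not by itself prevent such a selection, since a two-sided p-value does not depend on which coded group is VR. That makes prior specification worthwhile, but it is not evidence of bias.

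**Conclusion.** The point holds as a gap in specification that should be fixed. The named test cannot be run without a pairing rule that the plan lacks. Two readings open to an analyst (pairs that ignore blocks, and an unstratified rank-sum test) cost about 11 to 12 percentage points of power against block pairs (60 − 49 and 60 − 48) and are conservative, rejecting about 3% under the null. The two sound readings are almost equal in power with complete data and hold 5%, but give different significance verdicts in about one trial in ten.

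It would be wrong to conclude that pairing is invalid in this design or that the type I error rate is already compromised.

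A linked consequence is that 39 per arm does not give 70% power at d = 0.44 under either sound test. Power is about 45 to 60%, depending on the SD basis of 0.44. These figures rest on normal data, ρ = 0.3, two-sided testing and a single endpoint before the Benjamini-Hochberg step. The documents do not say how 0.44 relates to the 10% difference in the power statement, so the shortfall is stated for 0.44 only.

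**What to change.** Before any data by group are seen, amend the analysis sentence of IV.e in one of two ways.

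1. Preferred: for all continuous outcomes, replace the signed rank test with the surgeon-stratified Wilcoxon rank-sum (van Elteren) test. It uses every observed case and needs only the surgeon number, which is already collected. The cost is wording, plus somewhat less protection against within-surgeon time trends.
2. If the sponsor prefers to keep the signed rank test, add: *A pair is the two cases of one surgeon-specific randomisation block. A block with only one usable value for an endpoint is left out of that endpoint's test.* The phrase *usable value* is deliberate, so that blood loss and hospital stay are covered as well as the times. Record the envelope number for each case. The cost is wording, one extra data field, and the loss of observed patients in incomplete blocks.

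Do not simply rename the test in the sample-size sentence of IV.e. That would attach a 70% power claim to a test that does not reach it at 39 per arm for d = 0.44. Recompute the power for the chosen test, state the SD basis of 0.44, and restate the figure there and in the interim computation of IV.b, naming the same test in both places. As a guide, 70% power with block pairs at d = 0.44 on the total SD takes 47 pairs (94 patients), against the planned 78.

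### Section IV.e names no primary analysis for operative times: the signed rank comparison has undefined pairs and ignores case complexity, and the better-powered adjusted model is only additional

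*Combined protocol and SAP*

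**What the plan says.** Section IV.d on the design: "Each case will be assigned to one of the two preparation methods by a randomization procedure that is stratified by surgeon". There are four surgeon schedules in permuted blocks of 2. The within-surgeon correlation is set at 0.3, and the low value is chosen "given the wide variation in case complexity seen in our pilot study".

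Section IV.e on the comparison: "For continuous outcomes (e.g. various operative times), the nonparametric Wilcoxon signed rank test will be used for comparison". The sample-size statement in the same section uses that test for 70% power. Section IV.b repeats the target, saying that the interim recalculation is there so that the study "maintains 70% power to detect a 10% difference in the primary endpoint".

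The decision rule follows the Wilcoxon and Fisher tests directly: "The threshold of rejecting null hypothesis will be chosen at the conventional level of 0.05", with non-rejections to be reported as inconclusive. Benjamini-Hochberg control at 5% is stated in the paragraph before. Only then does the section introduce the regression: "To study the adjusted difference between case/control group, we will also use generalized linear mixed model". That model takes the Exhibit A covariates, a random surgeon effect and a Box-Cox transformed outcome, with QQ-plots as a check. The section ends with a repeated-measures ANCOVA, which is also described as testing the adjusted difference.

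Exhibit A ticks surgeon identifier, nephrometry score and mass size as covariates, and five operative times as primary endpoints.

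**The concern.** Three analyses could each supply the result for a given operative time, and the plan does not rank them. Because the power target, the threshold and the inconclusive rule stand with the Wilcoxon test, the natural reading is that this test decides.

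That test has two weaknesses here. First, signed rank is a paired test, but no pairs are defined. If it is run unpaired, it ignores the strata used in the randomisation, so between-surgeon variation stays in the error term. If it is run on the blocks of 2, surgeon is dealt with. Second, on either reading it makes no use of case complexity, which the plan itself describes as varying widely.

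At stake is a real effect reported as inconclusive although the data for a sharper test are already being collected. A choice among three tests also remains open once the data are seen.

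**Working it through.** **Inputs.** From Section IV.d: effect size d = 0.44, ρ = 0.3, four surgeons, blocks of 2, 39 per arm (78 in total). From Section IV.e: 0.05 threshold, 70% power. Assumptions, because the documents are silent:
- tests are two-sided;
- 0.44 is on the total SD (alternative below);
- ρ is the between-surgeon share of total variance;
- complexity explains a share R² of within-surgeon variance, with R² from 0 to 0.3.

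Power is for one test at 0.05, before Benjamini-Hochberg.

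**The plan's own figure.** The inflation reproduces: 34, 39 and 47 × 1.15 = 39.1, 44.9 and 54.1, printed as 39, 45 and 54; 2 × 39 = 78. The 34/39/47 row does not. Ignoring clustering, n = 2(1.960 + 0.524)²/0.44² = 63.8, so 64 per arm. Multiplying by the repeated-measures factor (1 + (m−1)ρ)/m with m = 3 gives 34.0, 42.5 and 51.0. That formula is linear in ρ, whereas the printed row rises by 5 and then 8. The cluster size is not stated. I therefore take 39 per arm as given.

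**Normal approximation.** Let k = 0.44 × √(39/2) = 1.943.
- Unadjusted: Φ(1.943 − 1.960) = 49.3%.
- Surgeon-adjusted: residual SD √0.7 = 0.837; 1.943/0.837 = 2.322; Φ(0.362) = 64.1%.
- Surgeon plus complexity: residual SD √(0.7(1 − R²)) = 0.794, 0.748, 0.700 at R² = 0.1, 0.2, 0.3; power 68.7%, 73.8%, 79.3%.
- Signed rank on 39 block pairs: the difference has SD √(2 × 0.7) = 1.183, so 0.44√39/1.183 = 2.322, as for the surgeon model. With rank efficiency 0.955, 2.322 × √0.955 = 2.269 and Φ(0.309) = 62%.

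**Type I error if unpaired.** The test scales by the total SD, but under stratified allocation the arm difference varies only with the within-surgeon SD. In large samples the error is 2[1 − Φ(1.960/0.837)] = 2[1 − Φ(2.343)] = 1.9%. Simulation with four surgeons gives about 2–3%.

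**Simulation** (4,000 trials per row; surgeons with 20/20/20/18 cases; normal outcome; Monte Carlo error about ±1.96√(0.6 × 0.4/4000) = ±1.5 points). Power, %:

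| Setting | Unpaired rank-sum | Signed rank, block pairs | Linear, surgeon | Linear, surgeon + complexity |
|---|---|---|---|---|
| ρ 0.3, R² 0 | 49.0 | 59.7 | 62.6 | 61.9 |
| ρ 0.3, R² 0.1 | 50.6 | 60.9 | 63.3 | 68.0 |
| ρ 0.3, R² 0.2 | 49.4 | 59.8 | 63.7 | 72.4 |
| ρ 0.3, R² 0.3 | 47.3 | 59.1 | 61.5 | 76.4 |
| ρ 0.1, R² 0.3 | 46.6 | 49.0 | 51.6 | 66.6 |
| ρ 0.3, R² 0.3, 0.44 on within-surgeon SD | 34.4 | 45.6 | 49.0 | 62.4 |

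Repeat simulations put the last column at about 67%, 73% and 76–79% for R² 0.1, 0.2 and 0.3, and the bottom row at about 35%, 45%, 47–50% and 61–62%.

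**Gains at ρ 0.3.**
- Over the unpaired test: 62.6 − 49.0 = 13.6 points from surgeon alone, and 76.4 − 47.3 = 29.1 with complexity at R² 0.3.
- Over block pairs: 62.6 − 59.7 = 2.9 and 76.4 − 59.1 = 17.3 (about 18 in a repeat).

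At ρ 0.1 and R² 0.3, the gains over the unpaired test fall to 5 and 20 points. Those over block pairs stay near 3 and 18.

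**The case against.** The strongest reply is that the plan names a paired test and randomises in surgeon-specific blocks of 2, so natural pairs exist. On that reading surgeon is used, the error rate is about 5%, and the surgeon-only model gains only about 3 points. This stands. A reader might infer that the planned test discards the surgeon strata, or that 14 to 29 points of power are simply lost. The documents do not support that, because the pairing is undefined, not absent by design. What remains is that the block-paired test still leaves complexity out.

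Second, covariate adjustment is already planned, in the mixed model and again in the ANCOVA, and no test is formally called decisive. This also stands. The defect is the missing ranking, not a missing model. The ANCOVA does not settle the matter: its covariates are not listed and its repeated measure is not identified, although each case is one operation.

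Third, the plan prefers a rank test because it does not need normality, and the simulations use normal outcomes only. So the advantage on skewed times is not shown here. The planned transformation and QQ-plots reduce that worry, and a rank-based sensitivity analysis covers what is left.

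Finally, a type I error of 2–3% is conservative. It costs power but does not make a positive result invalid.

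**Conclusion.** The point holds as one of unranked analyses, undefined pairing and unused complexity. At the plan's d and ρ, with d on the total SD, both rank-test readings fall short of 70%: about 48–50% unpaired and about 60% on block pairs. The surgeon-adjusted model reaches about 63%. Adding nephrometry score reaches 70% only if it explains roughly 20% or more of within-surgeon variance.

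A reader might infer that adjustment secures the stated power. It does not. R² is not in the documents, and neither is the SD behind 0.44. On the within-surgeon SD even the fullest model has about 61–62% at R² 0.3, and at ρ 0.1 it has about 67%. The ordering is firmer than the levels: in every setting examined where complexity matters, the model with surgeon and complexity has the most power. The change is worth making because it needs no extra patients.

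**What to change.** In Section IV.e, name one primary analysis for each primary operative time: a linear model of the transformed time (Box-Cox as planned, or log, fixed in advance) on arm, surgeon as a four-level factor, and nephrometry score, which Exhibit C lists as a preoperative parameter. State that the 0.05 threshold and the Benjamini-Hochberg rule apply to this analysis, and link the 70% power statement to it.

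Keep as sensitivity analysis either a surgeon-stratified rank test (van Elteren) or the signed rank test with pairs defined explicitly as the randomisation blocks. Label the mixed model with the full Exhibit A list as supportive, and either define or delete the repeated-measures ANCOVA.

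The cost is SAP wording; the covariates are already to be collected. The small downside is that the primary test then relies on a residual check, which the plan already makes with QQ-plots.
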